6.3.2 Criteria for Premature Termination or Suspension of Investigational Sites

A study site may be terminated prematurely or suspended if the site (including the investigator) is found in significant violation of Good Clinical Practice (GCP), protocol, or contractual agreement, is unable to ensure adequate study performance, or as otherwise permitted by the contractual agreement.

6.3.3 Procedures for Premature Termination or Suspension of the Study or the Participation of Investigational Site(s)

In the event that the sponsor, an IRB/independent ethics committee (IEC), or regulatory authority elects to terminate or suspend the study or the participation of an investigational site, a study-specific procedure for early termination or suspension will be provided by the sponsor; applicable investigational sites will follow the procedure during the course of termination or study suspension.

7.0 SUBJECT POPULATION

Screening for eligible subjects will be performed within 28 days prior to randomization or first dose.

7.1 Inclusion Criteria

Subject eligibility is determined according to the following criteria prior to entry into the study:

1. In the investigator's opinion, the subject can understand and sign the Informed Consent Form and comply with all protocol requirements.
2. The subject is a healthy male or female adult who is 18 to 55 years of age, inclusive at the time of ICF.
3. Subject weighs at least 45 kg (99 lbs) and has a BMI between 18.0 and 32.0 kg/m², inclusive at Screening.
4. A male subject who is nonsterilized* and sexually active with a female partner of childbearing potential* agree to use two forms of adequate contraception* from signing the ICF throughout the study and for 90 days after the last dose.

*Definitions and acceptable methods of contraception are defined in Section 9.1.13 Contraception and Pregnancy Avoidance Procedure, and reporting responsibilities are defined in Section 9.1.14 Pregnancy.

5. A female subject of childbearing potential who complies with contraception requirements* or a female with no childbearing potential, defined as the subject has been surgically sterilized (hysterectomy, bilateral oophorectomy, or tubal ligation) or who are postmenopausal (defined as continuous amenorrhea of at least 2 years and FSH>40 IU/L).

Note: hormonal contraceptives are not permitted as referenced in Table 3.

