10. Male subjects who do not agree to all the following rules: when sexually active with a female partner(s) of childbearing potential during the study, and for 90 days after the last dose of study drug: a) must use two acceptable methods of birth control (condom or surgical sterilization combined with highly effective method of contraception for the female partner) and b) refrain from sexual activity with female partners who do not use an acceptable method of birth control. Barrier contraception (condom) must be used by all-male subjects who were not surgically sterilized at least 90 days prior to screening. Male subjects must also agree to refrain from sperm donation during the study and until 90 days after the last dose of the study drug.
11. Female subjects who are pregnant or breastfeeding or plan to become pregnant or donate ova during the study or 30 days after the last dose of the study drug. Women of childbearing potential must agree to practice an acceptable method of birth control (e.g., , intrauterine device, barrier, abstinence).

Note: Hormonal contraceptives are not permitted as referenced in Table 3.

*Definitions and acceptable methods of contraception are defined in Section 9.1.13. Contraception and Pregnancy Avoidance Procedure and reporting responsibilities are defined in Section 9.1.14 Pregnancy.

--

12. Subject has previously had a seizure or convulsion (lifetime, with the exception of febrile seizures), including absence seizure.
13. Subject has current or recent (within 6 months) gastrointestinal disease that would be expected to influence the absorption of drugs (i.e., a history of malabsorption, any surgical intervention known to impact absorption [e.g., bariatric surgery or bowel resection], esophageal reflux, peptic ulcer disease, erosive esophagitis, or frequent [i.e., more than once per week] occurrence of heartburn).
14. Subject has a history of cancer or other malignancy, except for basal cell carcinoma or squamous cell carcinoma that has been in remission for at least 3 years prior to Day 1.

15. Subject has a positive test result for hepatitis B surface antigen (HBsAg), hepatitis C virus (HCV) antibody, or a human immunodeficiency virus infection at Screening.

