9.1.13 Contraception and Pregnancy Avoidance Procedure

From the date of signing of ICF, throughout the duration of the study, and for 30 days after the last dose of study medication, females of childbearing potential* must use **two** acceptable methods of contraception and must agree not to donate eggs; Nonsterilized** male subjects who are sexually active with a female partner of childbearing potential* must use **two** acceptable method(s) of contraception throughout the duration of the study, and for 90 days after the last dose of study medication. In addition, males must be advised not to donate sperm for 90 days after the last dose of study medication.

Females of childbearing potential are defined as any female who has experienced menarche and who has not undergone surgical sterilization (hysterectomy or bilateral oophorectomy) and is not postmenopausal.

Menopause is defined as at least 2 years since last regular menses with an FSH >40 IU/L or at least 5 years since last regular menses, confirmed before any study medication is implemented. Male subjects with potentially postmenopausal partners who are under the age of 55 years must use condoms unless their partner's postmenopausal status has been confirmed by FSH level.

**Sterilized males should be at least 90 days post-vasectomy and confirm that they have obtained documentation of the absence of sperm in the ejaculate.

Acceptable and highly effective methods of contraception are:

Note: hormonal contraceptives are not permitted as referenced in Table 3.

- Nonhormonal intrauterine device (IUD)
- Bilateral tubal occlusion
- Vasectomised subject/partner with documented azoospermia 90 days after procedure, if that partner is the sole sexual partner
- Same-sex intercourse, if used consistently for the duration of the study and post dosing as specified above

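### Tubal ligation is sterilization in Inclusion 5 but not in Section 9.1.13, and Exclusion 11 loosely asks women for one contraceptive method where Section 9.1.13 requires two

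*Protocol*

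**What the plan says.** Three places in the protocol govern contraception for female subjects.

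- **Section 7.1, Inclusion 5.** A woman may enter by one of two routes. Either she is of childbearing potential and meets the contraception requirements (marked with an asterisk that leads to Section 9.1.13), or she has no childbearing potential. The second route is open to women who are "surgically sterilized (hysterectomy, bilateral oophorectomy, or tubal ligation") or postmenopausal.
- **Section 9.1.13.** A woman is of childbearing potential if she has had menarche, "has not undergone surgical sterilization (hysterectomy or bilateral oophorectomy"), and is not postmenopausal. Such women must use two "acceptable methods of contraception and must agree not to donate eggs". The duty runs from consent through the study and "for 30 days after the last dose of study medication, females of childbearing potential" are held to it. The list headed "Acceptable and highly effective methods of contraception are" includes "Bilateral tubal occlusion". Complete abstinence is accepted with no second method.
- **Section 7.2, Exclusion 11.** "Women of childbearing potential must agree to practice an acceptable method of birth control", with the examples "intrauterine device, barrier, abstinence". A note below it refers to Section 9.1.13 for definitions and acceptable methods.

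The file holds two protocol texts. The wording compared here is from the one that bars all hormonal contraceptives (Section 7.3, Table 3). Both conflicts also stand in the other text.

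**The concern.** Eligibility turns on these words. Section 9.1.16 requires every inclusion criterion to be met and no exclusion criterion, and Section 13.2 allows no exemptions. If two sections define childbearing potential differently, two screeners can reach opposite decisions about the same woman and both can cite the protocol. A later monitor may then record a deviation for a subject who was admitted correctly under Inclusion 5.

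The singular in Exclusion 11 adds a second source of error. The criteria for men ask for two methods throughout (Inclusion 4, Exclusion 10, Section 9.1.13). Only the exclusion criterion for women speaks of one.

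What is at stake is pregnancy protection and consistent eligibility decisions in a first-in-human study in which hormonal methods are prohibited. It is not a matter of statistical inference.

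**Working it through.** No figure in the plan needs reproducing. The check applies each rule to the same woman and counts the methods she needs.

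**Step 1. Premenopausal woman with a tubal ligation and no other method.**

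- Inclusion 5: tubal ligation is in the sterilization list, so she has no childbearing potential. Further methods needed: 0.
- Section 9.1.13: tubal ligation is not in the sterilization list, so she is of childbearing potential and needs 2 methods. Tubal occlusion counts as 1. Further methods needed: 2 − 1 = 1.

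The two sections disagree by one method.

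**Step 2. Does the cross-reference settle step 1?** In Inclusion 5 the asterisk is attached to the contraception requirements, which belong to the first route of entry. The second route carries its own definition and no asterisk. A woman who enters by the second route never reaches the requirement to comply with Section 9.1.13. No sentence ranks one definition above the other, so the conflict remains.

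**Step 3. Woman of childbearing potential using an intrauterine device alone, or a barrier alone.**

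- Exclusion 11, by its wording: 1 method asked for, 1 present, so she is not excluded.
- Section 9.1.13: 2 methods required, so she is at least 1 short.
- Inclusion 5, first route: she must meet the Section 9.1.13 requirements and does not, so she fails.

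She fails an inclusion criterion and is not eligible under Section 9.1.16. The two texts differ (1 against 2), but the protocol as a whole resolves the difference in favour of two.

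**Step 4. Woman who elects complete abstinence.** Exclusion 11 and Section 9.1.13 both accept it alone. There is no conflict.

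| Woman | Section 7 criterion compared | Section 9.1.13 | Resolved by the protocol? |
|---|---|---|---|
| Tubal ligation only | 0 further (Inclusion 5) | 1 further | No |
| Device or barrier only | 1 in total (Exclusion 11) | 2 in total | Yes, through Inclusion 5 |
| Complete abstinence | Sufficient | Sufficient | No conflict |

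**The case against.** The strongest reply is that Section 9.1.13 plainly governs. Inclusion 5 and Exclusion 11 both point to it, and a careful site would apply the stricter text. For the number of methods this reply succeeds. A reader might infer from Exclusion 11 that a woman using only a barrier could validly be admitted. The documents do not support that: an exclusion criterion admits nobody, and such a woman fails Inclusion 5. What remains is a singular that should be brought into line.

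For tubal ligation the reply does not succeed. The note in Section 7.1 does mention definitions, but Inclusion 5 supplies its own for women without childbearing potential, and the asterisk is not placed there.

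A second reply is that the entry for tubal occlusion in the method list proves little, because the list also serves the female partners of male subjects. That is fair, and the entry alone would not show a conflict. The definition of childbearing potential in Section 9.1.13 shows it without the list.

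A third reply is that the practical risk is small, since tubal occlusion appears under a heading that calls the methods highly effective. This stands. The dispute is whether such a woman needs a second method, and her position is not comparable with that of a woman relying on a barrier alone.

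A reader might also want to size the problem by the time between the last scheduled pregnancy test and the end of the contraception duty. That interval is the same whichever wording applies, so it does not measure this inconsistency.

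**Conclusion.** The tubal-ligation conflict is real and the protocol does not resolve it: 0 further methods under Inclusion 5 against 1 under Section 9.1.13. The mismatch in Exclusion 11 (1 method against 2) is also real as wording, but it is secondary, because Inclusion 5 makes two the operative number. Its likely effect is screening error or an avoidable deviation.

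Severity is minor. The site can avoid harm by applying the stricter text, and no endpoint, analysis set, dose decision or sample size depends on the answer. The protocol gives neither the expected number of women nor the number with a tubal ligation, so the number affected is not estimated. The conclusion rests only on the wording of the three places and assumes that tubal ligation and bilateral tubal occlusion mean the same thing for this purpose.

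**What to change.** 1. Give tubal ligation or occlusion one status in Inclusion 5 and Section 9.1.13. The stricter option is to delete it from Inclusion 5 and keep it in Section 9.1.13 as one of the two methods. The alternative is to add it to the sterilization definition in Section 9.1.13 and remove it from the method list for female subjects.
2. In Exclusion 11, replace the single method with two acceptable methods as defined in Section 9.1.13, with complete abstinence alone as the stated exception.
3. Match the consent text to the revised wording.

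The cost is wording in three protocol places and the consent text. Under the stricter option a woman with a tubal ligation needs one further method, so the recruitment pool may be slightly smaller. Nothing in the design or analysis changes.

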7.2 Exclusion Criteria

Any subject who meets any of the following criteria will not qualify for entry into the study:

1. Subject has received any investigational compound within 30 days prior to the first dose of study medication or within 5 half-lives, whichever is greater.
2. Subject is a study site employee or an immediate family member of a study site employee.
3. Subject has evidence of CS neurologic, cardiovascular, pulmonary, hepatic, hematopoietic disease, renal, metabolic, gastrointestinal, urologic, immunologic, endocrine disease, serious allergy, full-body allergic skin rash (including hives), psychiatric disorder, evidence of abnormal liver function test, evidence of abnormal renal function tests or other abnormality that may impact the ability of the subject to participate or potentially confound the study results.

Note: Healthy volunteers with pre-existing stable disease, defined as diseases not requiring significant change in therapy or hospitalization for worsening disease during the 6 wks before enrolment, may be included at the discretion of the Investigator.

4. There is any finding in the subject's medical history, physical examination, or safety laboratory tests giving reasonable suspicion of a disease that would contraindicate taking CVN766 or a similar drug in the same class or that might interfere with the conduct of the study
5. Subject has a known hypersensitivity to any component of the formulation of CVN766.
6. Subject has a positive urine result for drugs of abuse at Screening or Inpatient Check-in (Day -1).
7. Subject has a history of a major psychiatric illness or currently receiving therapy for a psychiatric condition
8. Subject has a history of drug abuse or a history of alcohol abuse (more than 14 units/week) within 1 year prior to the Screening Visit or is unwilling to agree to abstain from alcohol and drugs throughout the study.
9. Subject has taken any excluded medication, supplements, or food products listed in the Excluded Medications and Dietary Products table as listed in [Table 3: Excluded Medications and Dietary Products](#).
10. Male subjects who do not agree to all the following rules: when sexually active with a female partner(s) of childbearing potential during the study, and for 90 days after the last dose of study drug: a) must use two acceptable methods of birth control (condom or surgical sterilization combined with highly effective method of contraception for the female partner) and b) refrain from sexual activity with female partners who do not use an acceptable method of birth control. Barrier contraception (condom) must be used by all-male subjects who were not surgically sterilized at least 90 days prior to screening. Male subjects must also agree to refrain from sperm donation during the study and until 90 days after the last dose of the study drug.
11. Female subjects who are pregnant or breastfeeding or plan to become pregnant or donate ova during the study or 30 days after the last dose of the study drug. Women of childbearing potential must agree to practice an acceptable method of birth control (e.g., , intrauterine device, barrier, abstinence).

Note: Hormonal contraceptives are not permitted as referenced in Table 3.

*Definitions and acceptable methods of contraception are defined in Section 9.1.13. Contraception and Pregnancy Avoidance Procedure and reporting responsibilities are defined in Section 9.1.14 Pregnancy.

--

12. Subject has previously had a seizure or convulsion (lifetime, with the exception of febrile seizures), including absence seizure.
13. Subject has current or recent (within 6 months) gastrointestinal disease that would be expected to influence the absorption of drugs (i.e., a history of malabsorption, any surgical intervention known to impact absorption [e.g., bariatric surgery or bowel resection], esophageal reflux, peptic ulcer disease, erosive esophagitis, or frequent [i.e., more than once per week] occurrence of heartburn).
14. Subject has a history of cancer or other malignancy, except for basal cell carcinoma or squamous cell carcinoma that has been in remission for at least 3 years prior to Day 1.

15. Subject has a positive test result for hepatitis B surface antigen (HBsAg), hepatitis C virus (HCV) antibody, or a human immunodeficiency virus infection at Screening.
16. Subject who regularly use nicotine-containing products (including but not limited to cigarettes, electronic cigarettes, pipes, cigars, chewing tobacco, nicotine patch, or nicotine gum). The casual users may participate but must agree to refrain from the time of Screening for the duration of the study or a positive urine cotinine test at Inpatient Check-in (Day 1).
17. Subject has poor peripheral venous access (defined as more than three failed attempts to cannulate).
18. Subject has donated or lost 450 mL or more of their blood volume (including plasmapheresis) or had a transfusion of any blood product within 45 days prior to Day 1.
19. Subject has an abnormal (CS) ECG at Screening or Inpatient Check-in (Day -1). Entry of any subject with an abnormal (NCS) ECG must be approved and documented by signature by the Investigator or medically qualified sub-investigator.
20. Subject has a supine blood pressure outside the ranges of 90 to 140 mm Hg for systolic and 40 to 90 mm Hg for diastolic, confirmed with repeat per PI discretion, at the Screening Visit or Inpatient Check-in (Day -1).
21. Subject has a resting heart rate outside the range of 40 to 100 bpm, confirmed with repeat per PI discretion, at the Screening Visit or Inpatient Check-in (Day -1).
22. Subject has a QT interval with Fridericia's correction method (QTcF) >450 ms (males) or >470 ms (females) or PR outside the range of 120 to 220 ms, confirmed with one repeat testing at the Screening Visit or Inpatient Check-in (Day -1) Visit.
23. Subject has abnormal Screening or Inpatient Check-in (Day -1) laboratory values that suggest a CS underlying disease or subject with the following lab abnormalities: ALT and/or AST >1.5 the ULN, confirmed with one repeat testing.
24. Subject has a risk of suicide according to the investigator's clinical judgment or has made a suicide attempt in the previous 2 years.

7.3 Excluded Medications and Dietary Products

Use of the agents in [Table 3](#) (prescription or nonprescription) is prohibited from the time points specified until completion of all study activities.

Table 3 Prohibited Medications and Dietary Products

28 days prior to Inpatient Check-in	7 days prior to Inpatient Check-in	72 hours prior to Inpatient Check-in
Prescription medications (including hormonal contraceptives)	OTC medications, including antacids, proton-pump inhibitors, and H2 receptor antagonists ^(a)	Products containing caffeine or xanthine (e.g., tea or coffee)
Nicotine-containing products	Vitamin supplements	poppy seeds
Nutraceuticals (e.g., St. John’s wort, ginseng, kava kava, ginkgo biloba, Chinese herbs, and melatonin)	Orexin receptor antagonists including suvorexant (Belsomra [®]), lemborexant (Dayvigo [®]), and related compounds	
Immunization/Vaccines ^(b)	Alcohol-containing products	
Known strong inhibitors/inducers of CYPs 3A4/5 ^(c)		

CYP= cytochrome P-450, OTC=over the counter.

- ^(a) Occasional use of acetaminophen (~1 g/day) and 400mg ibuprofen TDS when required or other medication as approved by the sponsor’s Medical Monitor on a case-by-case basis is allowed except on Day 1
- ^(b) Inclusive of but not limited to H1N1 and flu vaccinations. Subjects who have received the COVID-19 Vaccine between -10 and -28 days may participate provided they did not experience any side effects of any description. COVID-19 vaccine doses may be administered 7 days post-study medication dosing.
- ^(c) e.g., chloramphenicol, clarithromycin, ketoconazole.

Subjects must be instructed not to take any medications during study participation, including over-the-counter drug products, without first consulting with the investigator.

7.4 Diet, Fluid, Activity Control

Subjects will be confined to the clinic for each of the dosing days as well as a period of time sufficient to collect additional post-dose PK samples and monitor for safety and tolerability (Day -1 through Day 4 for single-dose cohorts and Day-1 through Day 9 for multiple-dose cohorts). During confinement, subjects will be provided 3 standard meals and a snack per day, each containing approximately 30% fat (relative to the total calories). The meals served on the day of dosing should be similar in nutritional content for each subject in the study. The study menu should be recorded and submitted to the study file with a copy provided to the sponsor prior to the start of the study. Breakfast will not be provided on dosing days until at least 1 hour after dose administration unless otherwise indicated (i.e., Days 2-6 for MAD cohorts). The meal start and stop times and percentage of the meal consumed will be recorded in the source and appropriate electronic case report form (eCRF) for all meals served on dosing days.

If a blood draw or any study procedure coincides with a meal, the blood draw will take precedence, followed by the study procedure and then the meal.

Subjects will remain in bed at a semi-supine position for 4 hours following the dose administration, except as necessitated by the occurrence of an AE or study procedures (e.g., obtaining a 12-lead ECG). Subjects must refrain from strenuous exercise from 72 hours before Inpatient Check-in and until check-out.

On the dosing days where extensive PK and/or CSF sampling is indicated (i.e., single-dosing Day 1 and first and last multiple-dose days, e.g., days 1 and 7), CVN766 or placebo suspension will be administered with approximately 240 mL of water after a fast of at least 10 hours. Subjects will continue to fast for an additional 4 hours after dosing and eat lunch following the 4-hour PK blood and CSF collection. Subjects may consume water ad libitum except for 1 hour before and 1 hour after drug administration.

For the food effect cohort (S3), single-dose administration will be administered after ingesting a standardized high-fat, high-calorie meal according to FDA Guidance for Industry (Food-effect bioavailability and fed bioequivalence studies, Dec 2002). Subjects will finish the entire content of their breakfast within 25 minutes and will receive an investigational product 30 minutes (± 5 minutes) after beginning the meal. The S3 (food effect) cohort meals may be staggered to ensure dosing occurs 30 minutes after the beginning of the meal.

Subjects will also fast for at least 10 hours prior to safety laboratory collection times as indicated. However, consumption of water as desired is permitted during this time, except for dosing days, as indicated above.

